**Data: 1/2/2022**

**SUMMARY:** The glycocalyx is a layer of macromolecules that covers the luminal surface of the endothelium, playing an important role in vascular homeostasis. Several studies have shown that in conditions of sepsis there is a degradation of the glycocalyx mediated by inflammatory mechanisms, releasing its components into the bloodstream. These glycocalyx fragments can be measured in blood plasma, showing a correlation between these markers and organ dysfunction, severity and mortality in sepsis situations. However, despite the great interest in glycocalyx biomarkers, their values in patients undergoing colorectal surgery are not well known. Therefore, verifying whether plasma levels of glycocalyx damage markers increase in the perioperative period of colorectal surgery is of great interest at the pathophysiological and clinical level, since the correlation of these markers with postoperative clinical evolution is unknown. In this study we want to determine the plasma levels of Heparan-sulphate and Syndecan-1, two of the most important constituents of the glycocalyx, and perform several measurements to form a "time course" of the plasma levels of these markers, in order to compare the different subgroups of patients undergoing colorectal surgery based on their clinical and surgical characteristics.

**BACKGROUND:**

The endothelial glycocalyx (EG) is a complex layer of macromolecules that lines the luminal surface of the vascular endothelium. This concept was proposed more than 70 years ago and its composition is well studied as detailed in two reviews (1, 2). However, its role in the mechanisms of endothelial protection and injury, and its subsequent clinical implications, have recently become evident. The GE consists of a variety of molecules, including glycoproteins and proteoglycans, that provide the basis for plasma-endothelial cell interaction. The structure of GE, although well characterized in vitro, is poorly defined in vivo because its composition changes dynamically by self-assembly and shear-dependent enzymatic degradation or detachment of its elements. Its major components are hyaluronic acid, proteoglycans (PG) such as syndecan-1, glycoproteins, plasma proteins and glycosaminoglycans (GAG), whose main component is Heparan Sulfate. The GE as a whole forms an endothelial surface layer that acts as a barrier to circulating cells and large molecules. Considerable prognostic-therapeutic promise lies in the emergence of the EG as a key mediator of endothelial dysfunction in pathogenic states, particularly with respect to vascular permeability and edema formation. Several studies have demonstrated the role of GE in plasma/interstitial fluid balance (3,4,5), mechano-transduction that couples intravascular pressure, and endothelial cell responses, i.e., biochemical signals, (6) to the inflammatory response cascade (7,8,9). EG damage affects a number of important endothelial cell functions leading to impaired mechano-transduction with changes in fluid passage (6,10), activation of

coagulation pathways (11), leukocyte adhesion (7,11 ) and platelets (12) to the surface of endothelial cells, and leakage of fluid and plasma proteins into the interstitium (13,14), resulting in tissue edema (15). The specific pathophysiological triggers that lead to EG damage are still actively investigated and remain poorly understood. Nevertheless, EG protection appears to be a promising target in many clinical scenarios, especially since its degradation is closely associated with the pathophysiology of inflammation, capillary leak, and edema formation in various injuries and disease states; including ischemia/reperfusion, hypoxia, inflammation, trauma, hypervolemia, atherosclerosis, diabetes, and hypertension (16). In patients undergoing major abdominal surgery (including digestive, urological, gynecological or other surgery) there is very little information on the potential endothelial damage secondary to surgery (19). There are some reviews that have studied the damage of the SG in septic patients of medical and surgical origin (17, 18). However, in relation to digestive abdominal surgery, and specifically in colorectal surgery, only one study has been carried out, with only 18 patients undergoing colectomy (without mentioning the pathologies) and they are included with other patients of major abdominal surgery of the pancreas, liver, gynecology and urology (19).

#### **EXPECTED RESULTS:**

In this study, it is expected that in the patients who underwent elective surgery, the markers of glycocalyx damage will increase their values in the postoperative laboratory tests compared to the values of the baseline (control) laboratory tests. It is equally expected that in patients undergoing urgent surgery, generally in clinical states of occlusion, perforation or sepsis, with activation of the inflammatory response, dehydration with decreased oncotic pressure and generation of tissue edema and third space, the markers of damage of glycocalyx are already elevated in the baseline analysis, with a maintenance or greater elevation of its values in the postoperative period. Likewise, a correlation would be expected between glycocalyx damage markers and other markers involved in the inflammatory response, such as leukocytes, C-reactive protein, procalcitonin, and lactate; as well as with associated patient comorbidities that lead to endothelial degeneration, such as high blood pressure, obesity, diabetes, atherosclerosis, etc. If the results of this study were as expected, glycocalyx damage markers (Heparan sulfate and Syndecan-1) could be used together with other inflammatory markers (CRP, procalcitonin, etc.) and be very useful in postoperative follow-up. of surgical patients, being able to anticipate possible postoperative complications. However, if elevations in glycocalyx markers were not observed in the perioperative period, it could be due to a lack of the number of Time-course determinations; that is to say, that an elevation of markers did occur, but we would not have detected it in the measurement times; or a larger

study population might also be needed. In either case, the study could be completed in subsequent research projects.

## **OBJECTIVES**

**Primary Objectives:** To estimate the plasma levels of the 2 most representative markers of damage to the endothelial glycocalyx (Heparan-sulfate and Syndecan-1) in patients undergoing colorectal surgery during the perioperative period (“time-course”).

### **Secondary Objectives:**

- To analyze a possible correlation of the glycocalix damage markers with other analytical parameters (PCR, procalcitonin, lactate, complete blood count, coagulation and basic biochemistry).
- To analyze the possible relationship of glycocalyx damage markers with different parameters depending on the patient (age, sex and associated comorbidities) and the surgical intervention (surgical time, approach, type of surgery...).
- To analyze other clinical parameters that may indicate a possible postoperative complication and their relationship with markers of endothelial glycocalyx damage will also be studied.

**METHODOLOGY DESIGN:** The present work is about a clinical, prospective, observational, and longitudinal study of single center groups (Hospital Lluís Alcanyís, Xàtiva). Always after the approval of the Research Ethics Committee of said Hospital.

**STUDY POPULATION:** The study population (value of n) has been calculated on a population of 100 patients who will undergo surgery approximately one year. With a confidence level of 95% and a margin of error of 5%, a sample size of 80 patients has been calculated. These 80 patients will be of legal age, men and women, undergoing elective or emergency colorectal surgery (right hemicolectomy, extended right hemicolectomy, left hemicolectomy, sigmoidectomy, anterior resection of the rectum or abdominoperineal amputation).

**CHOICE OF PATIENTS AND INFORMED CONSENT:** The selection of patients and the drafting of the informed consent documents will be carried out in a reasoned manner as established in article 32 of the Declaration of Helsinki and in article 58.2 of the Research Law. Biomedical. It should be considered taking into account the Declaration of Helsinki of the World Medical Association in its latest revision. And according to its latest version of the Helsinki Declaration of Fortaleza (Brazil) October

2013. Patients will be included in the study upon preoperative hospital admission, after verifying compliance with the inclusion criteria. To participate, it will be necessary to sign the informed consent.

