#### **METHOD:**

Blood samples will be drawn from an intravenous line, in BD Vacutainer® LH PST™ II tubes with lithium heparin at different times: 1st) basal time (preoperative), at hospital admission; 2nd) 2 hours after the end of the surgery, 3rd) 6 hours after the end of the surgery, 4th) 24 hours after the end of the surgery and 5th) 48 hours after the surgery. The blood samples will be centrifuged at 3000 rpm/12 min and the supernatants will be collected and stored at -80°C until the determination of the markers. Plasma levels of Syndecan-1 and Heparan Sulfate will be determined by ELISA (Enzyme-Linked Immunosorbent Assay), PCR (C-reactive protein), procalcitonin, lactate, blood count, renal function, basic coagulation and general biochemistry techniques. The blood samples will be drawn by the nursing team of the general surgery hospitalization ward, and will be transported to the laboratory by the auxiliary staff of said hospitalization ward. The laboratory staff will be in charge of centrifuging the samples and storing the supernatants in the pertinent conditions mentioned above. Later, when all the samples have been collected, the determination of the markers will be carried out, and the result will be displayed through the Orion clinic computer program or in paper format, which will be delivered to me personally. In addition, all the usual anesthetic, surgical and

postoperative care protocols of the Institution (General and Digestive Surgery Department. Lluís Alcanyís Hospital) will be maintained for these patients.

**STATISTICAL ANALYSIS PLAN (SAP):** Continuous data are expressed as mean  $\pm$  standard deviation. The normality of the data obtained was determined with the Kolmogorov-Smirnov and Shapiro-Wilk tests. Differences between baseline values and different moments after the "time course" of plasma levels of glycocalyx damage markers and other parameters will be analyzed by one-way analysis of variance (ANOVA). Data sets in which F is significant will be examined for multiple comparisons by Tukey's test. The Pearson correlation coefficient (r) will be calculated between the values of the EG damage markers and other parameters. The possible differences between the different population subgroups will be examined with the Student's t-test.  $P < 0.05$  will be considered statistically significant. All statistical calculations will be performed using the SPSS program.

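### The 5% margin of error behind n = 80 is not shown to be the precision of the marker levels that the study sets out to estimate

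*Combined protocol and SAP*

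**What the plan says.** The sample size is justified in the Study Population paragraph alone. The number "has been calculated on a population of 100 patients who will undergo surgery approximately one year", and then: "With a confidence level of 95% and a margin of error of 5%, a sample size of 80 patients has been calculated". No formula is named, and nothing says whether the 5% means percentage points of a proportion or percent of a mean.

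The primary objective is "To estimate the plasma levels of the 2 most representative markers of damage to the endothelial glycocalyx", heparan sulfate and syndecan-1, over the perioperative time course in patients having colorectal surgery. The SAP treats these as continuous: "Continuous data are expressed as mean" with the standard deviation, followed by one-way ANOVA, Tukey's test, Pearson correlation and Student's t-test. It mentions no finite-population correction.

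The combined document gives no SD or CV for either marker and no expected proportion, and it names no proportion as a primary outcome.

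**The concern.** For a study whose primary aim is estimation, precision is the natural basis for the sample size, and the 5% is the only precision figure in the plan. It is attached to no quantity. The inputs that yield 80 are the usual ones for a proportion in a small finite population, while the study estimates mean concentrations. A reader could reasonably take the 5% as the precision of the marker means, and nothing in the document shows that.

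The population matters too. A calculation on 100 patients gains much of its apparent precision from sampling most of them. The Primary Objectives refer to colorectal surgery patients without limiting them to one year's list, and the Summary gives as motivation that "their values in patients undergoing colorectal surgery are not well known". If the wider population is meant, the gain from the correction does not apply.

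**Working it through.** **Inputs from the Study Population paragraph:** N = 100, 95% confidence (z = 1.96), margin e = 0.05, stated n = 80. **Assumed, because not stated:** p for a proportion, or CV for a mean.

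**1. Reproduce 80 as a proportion, p = 0.5.**
- n0 = z² p(1−p)/e² = 1.96² × 0.25/0.05² = 384.16
- n = n0/(1 + (n0 − 1)/N) = 384.16/(1 + 383.16/100) = 79.51, rounded up to 80

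The shortcut N/(1 + N e²) = 100/(1 + 100 × 0.0025) also gives 80. With p = 0.4, n0 = 368.79 and n = 78.84, so 79. The match therefore needs p at or close to 0.5.

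**2. Reproduce 80 as a mean.** With CV 0.5 and a margin of 5% of the mean, n0 = (1.96 × 0.5/0.05)² = 384.16, the same n0 and so the same 80. The stated inputs cannot tell the two readings apart. Each needs one unstated value and the finite-population correction.

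**3. Remove the correction and keep the other inputs, n = 80.**
- Proportion of 0.5: 1.96 × √(0.25/80) = 0.110, about 11 percentage points
- Mean with CV 0.5: about 11% of the mean (step 4)

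**4. Precision of a mean from 80 samples, no correction.**
- Half-width = t(0.975, 79)/√80 = 0.2225 SD
- Largest CV at which this is within 5% of the mean: 0.05/0.2225 = 0.225, about 22%

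**5. The same with the correction.**
- Factor √((100 − 80)/(100 − 1)) = √(20/99) = 0.4495
- Half-width = 0.2225 × 0.4495 = 0.100 SD
- CV limit for 5%: 0.05/0.100 = 0.50

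**6. Half-width as a percentage of the mean level, over an assumed range of CVs.**

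| Assumed CV | No correction | With correction (N = 100) |
|---|---|---|
| 50% | 11.1% | 5.0% |
| 75% | 16.7% | 7.5% |
| 100% | 22.3% | 10.0% |

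Using z in place of t changes these figures only slightly (0.219 SD and 0.098 SD). The document gives no CV with which to choose a row.

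**The case against.** The best defence is that this is a single-centre observational study with no confirmatory hypothesis and no power claim, so a pragmatic sample size is acceptable and the gap is one of reporting. That stands as far as the number of patients and the conduct are concerned. It does not cover the 5%, because the plan presents 80 as calculated from it.

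The proportion formula is an inference, since the plan names none, and a mean with CV 0.5 gives the same answer. That also stands: a reader might infer that the wrong formula was used, and the document does not prove it. What remains is that either reading needs an input the plan does not give.

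The plan does name its 100 patients. The remark in Expected Results that the markers could "be very useful in postoperative follow-up. of surgical patients" concerns possible later use and does not define the target population. Both points are fair. The stronger evidence is the primary objective, which is not confined to one year's patients, and the SAP, whose tests carry no correction.

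Expected Results also says that, if no elevation is seen, a larger "study population might also be needed". It would be tempting to say that such a result cannot be interpreted without a planned precision. That goes too far: confidence intervals computed from the final data would show how informative a flat result is, whatever margin was planned.

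Finally, any replacement figure has its own conditions. The 0.10 SD figure needs random sampling from the 100, whereas the plan describes consenting patients who meet the inclusion criteria. A CV for a level says nothing about the SD of a change. Withdrawal is allowed, so 80 complete samples are not assured. All three stand and are reflected in the fix.

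**Conclusion.** The concern holds in a limited form. The 5% margin is not shown to be the precision that the design delivers for its own objective. The number 80 reproduces only with a finite-population correction and an unstated p, or CV, of about 0.5. Without the correction the same inputs give about 11%, and 5% of a mean is reached only if the CV is about 22% or less.

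A reader might infer that 80 is too few, or that it is an arithmetic error. The document supports neither. The arithmetic is sound under the inputs just described, and adequacy depends on marker variability and on the population of inference, which the plan does not settle.

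The 0.22 SD figure rests on 80 patients with a sample at the time point in question, all patients pooled. The percentages rest on assumed CVs and apply to levels only.

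**What to change.** Keep n = 80. In the Study Population paragraph, replace the 5% margin with a statement such as:

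> Eighty patients with a sample at a given time point give a 95% CI half-width of about 0.22 SD for the mean level of a marker; for a within-patient change, the half-width is about 0.22 SD of that change.

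Then:
- For levels only, use a sourced CV for each marker if the sponsor has one. Otherwise show the assumed range: about 11%, 17% and 22% of the mean at CVs of 50%, 75% and 100%.
- Note that fewer complete samples widen the interval.
- State the population of inference. Leave out the finite-population correction unless the plan says that inference is limited to the one-year cohort of 100 and that the 80 are a random sample of it. Only then is the half-width about 0.10 SD.

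The cost is one reworded paragraph, with no extra patients and no change to conduct or analysis. The downside is that the stated precision becomes less favourable than 5% unless the marker CV is about 22% or less, or about 50% or less under the restricted cohort reading.

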#### **INCLUSION CRITERIA:**

To be included in the study, the following criteria must be met:

- Signature of the informed consent document.
- Age equal to or greater than 18 years.
- ASA surgical risk  $\leq$  III.
- Being operated on for colorectal surgery

#### **EXCLUSION CRITERIA:**

The presence of any of the following criteria will be excluding:

- Younger than 18 years old
- Pregnant women

#### **WITHDRAWAL FROM THE STUDY:**

Patients will be withdrawn from the study when any of the following events occur:

- Non-compliance inclusion criteria
- Due to voluntary abandonment of the patient

#### **METHOD:**

Blood samples will be drawn from an intravenous line, in BD Vacutainer® LH PST™ II tubes with lithium heparin at different times: 1st) basal time (preoperative), at hospital admission; 2nd) 2 hours after the end of the surgery, 3rd) 6 hours after the end of the surgery, 4th) 24 hours after the end of the surgery and 5th) 48 hours after the surgery. The blood samples will be centrifuged at 3000 rpm/12 min and the supernatants will be collected and stored at -80°C until the determination of the markers. Plasma levels of Syndecan-1 and Heparan Sulfate will be determined by ELISA (Enzyme-Linked Immunosorbent Assay), PCR (C-reactive protein), procalcitonin, lactate, blood count, renal function, basic coagulation and general biochemistry techniques. The blood samples will be drawn by the nursing team of the general surgery hospitalization ward, and will be transported to the laboratory by the auxiliary staff of said hospitalization ward. The laboratory staff will be in charge of centrifuging the samples and storing the supernatants in the pertinent conditions mentioned above. Later, when all the samples have been collected, the determination of the markers will be carried out, and the result will be displayed through the Orion clinic computer program or in paper format, which will be delivered to me personally. In addition, all the usual anesthetic, surgical and

postoperative care protocols of the Institution (General and Digestive Surgery Department. Lluís Alcanyís Hospital) will be maintained for these patients.

**STATISTICAL ANALYSIS PLAN (SAP):** Continuous data are expressed as mean  $\pm$  standard deviation. The normality of the data obtained was determined with the Kolmogorov-Smirnov and Shapiro-Wilk tests. Differences between baseline values and different moments after the "time course" of plasma levels of glycocalyx damage markers and other parameters will be analyzed by one-way analysis of variance (ANOVA). Data sets in which F is significant will be examined for multiple comparisons by Tukey's test. The Pearson correlation coefficient (r) will be calculated between the values of the EG damage markers and other parameters. The possible differences between the different population subgroups will be examined with the Student's t-test.  $P < 0.05$  will be considered statistically significant. All statistical calculations will be performed using the SPSS program.

**MEDIA:** We have sufficient infrastructure and biochemical laboratory reagents, as well as an ELISA reader. We also have all the consumable material necessary for the determination of glycocalyx damage markers, as well as all other biochemical determinations.

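### Heparan sulfate, a primary marker, is assayed in lithium-heparin plasma with no planned check that the tube additive does not cross-react in the ELISA

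*Combined protocol and SAP*

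**What the plan says.** The primary objective, under OBJECTIVES, is "To estimate the plasma levels of the 2 most representative markers of damage to the endothelial glycocalyx (Heparan-sulfate and Syndecan-1") over the perioperative period. METHOD sets five sampling times: baseline at admission, then 2, 6, 24 and 48 hours after surgery. Blood is drawn into "tubes with lithium heparin at different times". After centrifugation "the supernatants will be collected and stored at -80°C until the determination of the markers". Then "Plasma levels of Syndecan-1 and Heparan Sulfate will be determined by ELISA". No other tube type is named. The assays are run only once sample collection is complete.

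BACKGROUND places the analyte in its chemical class: "glycosaminoglycans (GAG), whose main component is Heparan Sulfate".

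No section names an ELISA kit, antibody or assay format, an accepted sample matrix, a figure for heparin cross-reactivity, a spike/recovery test or a comparison of tube types. MEDIA says only that reagents, consumables and an ELISA reader are available.

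**The concern.** The collection tube adds to every sample a compound from the same family as the analyte. That heparin, like heparan sulfate, is a sulfated glycosaminoglycan is basic chemistry; the documents do not discuss it. An ELISA selective for heparan sulfate may ignore heparin. One that is less selective will read part of it as analyte. The plan gives no means of telling which applies.

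Three features raise the stakes.

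- The primary objective is to estimate levels, and an added signal biases levels directly.
- The amount of heparin per mL depends on how full each tube is. Any cross-reaction would therefore vary between tubes and act as measurement error in the ANOVA, the t-tests and the Pearson correlations.
- The problem would surface late. With 80 patients and five samples each, up to 80 × 5 = 400 samples could be in the freezer before the first heparan sulfate result is seen. EXPECTED RESULTS attributes a possible null finding to too few time points or too small a population. Assay interference is not on that list, so an artefact could be taken for biology.

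**Working it through.** **No figure to reproduce.** The plan gives no heparin content, cross-reactivity or expected heparan sulfate level. What follows shows which planned quantities an interference would affect. All numerical inputs are assumptions.

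**Model.** Observed value = T + O. T is the true heparan sulfate level, with baseline mean μ and between-patient CV c. O is the apparent signal from the tube, with mean kμ and tube-to-tube CV v, independent of T and additive within the assay's working range. Assumed: c = 50%; v = 10% or 30%; k from 0 (no cross-reaction) to 10.

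**1. Levels.** Reported mean ÷ true mean = (μ + kμ)/μ = 1 + k. For scale, the 95% half-width for a mean with n = 80 and k = 0 is 1.96 × 0.5/√80 = 0.110 of the true mean. An offset of k = 0.1 would thus bias the level by about as much as the whole sampling uncertainty.

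**2. Absolute changes, constant offset (v = 0).** (T at time t + O) − (T at baseline + O) = change in T. The offset cancels. Adding the same constant to every value also leaves the ANOVA F, the Tukey and t-test differences, and Pearson r unchanged.

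**3. Noise, varying offset (v > 0).** In units of μ, the between-patient SD rises from c to √(c² + (kv)²). Correlations with another parameter shrink by the factor A = c/√(c² + (kv)²). Unpaired standardised differences shrink by the same factor. Example, k = 1 and v = 30%: A = 0.5/√(0.25 + 0.09) = 0.5/0.583 = 0.86.

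| k | reported ÷ true level | A, v = 10% | A, v = 30% |
|---|---|---|---|
| 0 | 1 | 1.00 | 1.00 |
| 0.1 | 1.1 | 1.00 | 1.00 |
| 0.5 | 1.5 | 1.00 | 0.96 |
| 1 | 2 | 0.98 | 0.86 |
| 5 | 6 | 0.71 | 0.32 |
| 10 | 11 | 0.45 | 0.16 |

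Levels are sensitive even to a small k. Comparisons and correlations suffer materially only when k is large or tube filling is uneven. At k = 0 nothing changes. The documents do not say which row applies.

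**The case against.** The strongest reply is that the harm depends on an unnamed kit. It may accept heparin plasma and have negligible cross-reactivity, in which case there is no effect. That stands, and it is why the point is a compatibility question still to be settled and not a demonstrated measurement error.

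A second reply is that the tube type is the same at every draw and the SAP compares absolute means, so a constant offset drops out. That also stands for the ANOVA, the t-tests and the correlations. It does not rescue the levels themselves, and it does not cover variation in filling.

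A reader might go further in four ways that the documents do not support.

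- *The additive swamps the assay and the marker is lost.* Suppose tube heparin of 50–200 µg/mL and plasma heparan sulfate of 0.01–5 µg/mL, both assumed. The ratio then runs from 50/5 = 10 to 200/0.01 = 20,000. So wide a range settles nothing, and the cross-reactivity that would turn it into a signal is unknown and may be zero.
- *A true doubling would read as +50%.* With an offset equal to baseline, (2 + 1)/(1 + 1) = 1.5. But the SAP computes no ratios.
- *Both markers are compromised.* The argument rests on chemical kinship between heparin and heparan sulfate and does not carry over to Syndecan-1.
- *Heparin given in care biases the time course.* METHOD keeps the usual "postoperative care protocols of the Institution", and the documents do not say whether these involve heparin. It would be a separate source, present with any tube type. Since emergency patients are eligible, it need not be confined to later samples. Repeating the analysis without samples drawn after heparin could remove most postoperative data.

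**Conclusion.** The concern holds as a conditional one. One of the two primary markers is to be measured in plasma containing a close chemical relative of the analyte, and nothing in the plan shows that the assay can tell them apart. If it cannot, the heparan sulfate levels are biased and uneven tube filling adds noise to comparisons and correlations. Absolute within-patient changes are protected to the extent that the offset is constant and additive. The size cannot be computed from the documents; the table in the working is an illustration on assumed inputs and starts at no effect. The point merits a change because the check is cheap, the assays are left to the end of collection, and the levels are the stated objective. It does not show that the heparan sulfate results will be invalid.

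**What to change.** In METHOD:

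- Name the heparan sulfate ELISA kit and the sample types it accepts.
- Collect the heparan sulfate aliquot in a non-heparin tube, for example EDTA, that this kit accepts. Use the same tube type at all five times.
- If lithium heparin is kept, or samples are already frozen, show non-interference before the study samples are assayed. Acceptable evidence is the kit's stated heparin cross-reactivity and sample matrix, a spike/recovery test, or paired samples in both tube types.
- Record whether and when heparin was given before each sample, as a descriptive variable only. This changes no care and calls for no exclusion analysis.

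Syndecan-1 needs no change on this argument.

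The cost is possibly one more tube at each draw, or a small pre-assay check. The added burden may be less, because METHOD also lists a blood count and coagulation tests. These are not normally run on lithium-heparin gel plasma, so a non-heparin tube may already be drawn. The documents do not give enrolment status. If collection has begun, the non-interference route is the one available for samples already stored.

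### Tukey's test adjusts for all 10 pairs of sampling times, although the SAP's stated comparison is the 4 contrasts with baseline: valid, but more conservative than the question needs

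*Combined protocol and SAP*

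**What the plan says.** The METHOD section lists five blood samples: "1st) basal time (preoperative), at hospital admission; 2nd) 2 hours after the end of the surgery, 3rd) 6 hours after the end of the surgery", then "4th) 24 hours after the end of the surgery and 5th) 48 hours after the surgery".

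The STATISTICAL ANALYSIS PLAN paragraph describes the time analysis as "Differences between baseline values and different moments after" and assigns it to a one-way ANOVA. The follow-up is: "Data sets in which F is significant will be examined for multiple comparisons by Tukey's test". The significance level is 0.05, with no statement on sidedness.

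EXPECTED RESULTS states the hypothesis for elective patients: the markers "will increase their values in the postoperative laboratory tests compared to the values of the baseline (control) laboratory tests". For urgent patients it expects a baseline that is already raised, and values that stay there or go higher.

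The primary objective is to estimate heparan sulfate and syndecan-1 over the perioperative time course. No section poses a hypothesis that compares one postoperative time with another, restricts Tukey's test to the pairs that include baseline, or gives a reason for all-pairs control.

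**The concern.** The stated question and the multiplicity adjustment do not match. The question is whether each later sample differs from baseline, which is four contrasts per marker. Tukey's test protects a family of ten, and the other six (24 h against 48 h, for example) correspond to no stated hypothesis. A larger family means a larger critical value, so a true change from baseline is missed more often and the intervals around it are wider than they need be.

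This matters here because EXPECTED RESULTS already discusses failing to detect an elevation and names a larger study population as one possible remedy. Recruiting more is not easy: the 80 patients come from about 100 operated on in roughly a year at one centre. An adjustment matched to the question recovers some power without further patients or assays.

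**Working it through.** **Inputs from the documents.** Five sampling times (METHOD); 80 patients (STUDY POPULATION); significance level 0.05 (SAP).

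**Assumptions, not in the documents.** Two-sided tests; complete data; equal variances; correlation 0.5 between contrasts, which follows from the shared baseline when variances and within-patient correlations are equal.

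**The plan's own figure.** The sample size reproduces as a survey-proportion calculation with finite-population correction, if a proportion of 0.5 is assumed:
- n0 = 1.96² × 0.5 × 0.5 / 0.05² = 384.1
- n = 100 × 384.1 / (99 + 384.1) = 79.5, rounded up to 80

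No effect size, SD or power enters it, so the power comparisons below are relative.

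**Number of comparisons.** All pairs: 5 × 4 / 2 = 10. With baseline: 4. Between postoperative times: 10 − 4 = 6.

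**Error degrees of freedom.** One-way ANOVA: 5 × 80 − 5 = 395. Repeated measures: (80 − 1) × (5 − 1) = 316.

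**Critical values of |t|.** Tukey is the 95% point of the studentized range for five means, divided by √2. Dunnett is for four contrasts with correlation 0.5, by numerical integration. Holm's first step is Bonferroni at 0.05/4.

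| Error df | Tukey | Dunnett | Holm, first step |
|---|---|---|---|
| 395 | 2.740 | 2.452 | 2.509 |
| 316 | 2.744 | 2.454 | 2.512 |

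The choice of df hardly matters.

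**Familywise error.** With a correct error term, Tukey's cutoff applied to the four baseline contrasts gives about 2.3%. The per-comparison p-value needed is 0.0064 under Tukey and 0.0147 under Dunnett.

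**Interval width.** 2.744 / 2.454 = 1.118, so Tukey intervals are about 12% wider than Dunnett intervals.

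**Power.** If a contrast has 80% power at critical value c, its power under Tukey is about Φ(c + 0.842 − 2.744), and the ratio of sample sizes for equal power is ((2.744 + 0.842) / (c + 0.842))². For 90%, 1.282 replaces 0.842.
- Dunnett at 80%: Φ(2.454 + 0.842 − 2.744) = Φ(0.552) = 71%; ratio (3.586 / 3.296)² = 1.18
- Dunnett at 90%: Φ(0.992) = 84%; ratio (4.026 / 3.736)² = 1.16
- Holm's first step at 80%: Φ(2.512 + 0.842 − 2.744) = Φ(0.610) = 73%; ratio (3.586 / 3.354)² = 1.14

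Holm's later steps use smaller critical values, so the Holm comparison is at its strictest.

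**Two markers.** At 5% per marker, the error over both is up to 1 − 0.95² = 9.8% if they are independent. Under Tukey's cutoff it is 1 − (1 − 0.0228)² = 4.5%. Dunnett at 2.5% per marker has critical value 2.71; where that has 80% power, Tukey has Φ(2.711 + 0.842 − 2.744) = Φ(0.809) = 79%.

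**Relation to the error term.** In a simulation (80 patients, assumed within-patient correlation 0.5, assumed rise of 0.35 SD at all later times), power for the 2 h contrast was:

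| Error term | Tukey after a significant F | Dunnett |
|---|---|---|
| One-way ANOVA | 22% | 36% |
| Repeated measures | 65% | 75% |

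The requirement of a significant F cost about 1 percentage point or less in the Tukey column.

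**The case against.** The strongest case for leaving the plan alone has five parts.

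- *Tukey is valid.* This stands. A reader might infer that the mismatch inflates false positives; it does the opposite. The issue is efficiency.
- *All-pairs comparisons serve the primary objective.* The objective is to estimate a time course, and peak and return are part of describing one. This stands in part. A reader might infer that the extra six comparisons buy nothing at all, but the time-course objective does not support that. Still, describing a course needs estimates and intervals rather than formal tests between postoperative times, and the SAP's own sentence is confined to changes from baseline.
- *The gain depends on spending 5% on each marker.* Correct: splitting 5% over the two markers nearly removes it. However, the plan claims no control across markers under either method, so a per-marker 5% keeps its present level of claim. It should be stated openly.
- *The loss is hypothetical.* A reader might take 71% as this study's power, or conclude that the study is underpowered. The documents give no effect, SD or power from which to say either. The critical values and the 2.3% need no effect size, though they do rest on the variance assumptions.
- *The one-way error term costs more.* True in the simulation: correcting it moves Tukey from 22% to 65%, and Dunnett then adds 10 points. The mismatch remains after that correction, but the two changes belong together.

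In addition, the first explanation in EXPECTED RESULTS for a missed elevation is the choice of sampling times, which no critical value repairs.

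**Conclusion.** The point holds as a moderate loss of efficiency. For the four contrasts that the SAP frames, Tukey's test uses a familywise error of about 2.3% where 5% is available. The cost is about 9 percentage points of power where Dunnett would have 80%, or about 7 points against Holm's first step. Equal power at 80% would need about 18% or 14% more patients respectively.

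These figures assume two-sided tests, equal variances, correlation 0.5 between contrasts, a correct within-patient error term and 5% per marker. They compare methods and contradict no figure in the documents. The change is worth making because it is cheap, and because the ANOVA sentence beside it needs revision for the repeated samples anyway.

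**What to change.** Replace the ANOVA and Tukey sentences of the SAP with text along these lines:

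*Each marker is analysed with a repeated-measures or mixed model that accounts for the five samples from the same patient. The four within-patient contrasts with baseline (2, 6, 24 and 48 h) are prespecified and tested two-sided, with Dunnett or Holm adjustment at 5% per marker. No control of error across the two markers is claimed. Differences between postoperative times are reported descriptively with confidence intervals.*

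The final SAP should name one of the two adjustments. Dunnett gives the smaller critical value at the first step but relies on the assumed correlation between contrasts; Holm needs only the four p-values.

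The cost is a rewrite of two adjoining sentences, with no added patients, samples or assays. The downside is that peak and recovery between postoperative times are not formally tested. If the investigators want those tests, the SAP should state that hypothesis, and all-pairs control would then have a purpose.
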